Exclusion criteria:	
1. Have received the following prior or current anticancer therapy:
a. Radiotherapy within the last 6 weeks (except for symptom control and where the lesions will not be used as measurable disease)b. Endocrine therapy during the previous 4 weeks except for luteinizing hormone releasing hormone (LHRH) agonists for prostate cancerc. Chemotherapy during the previous 4 weeksd. Immunotherapy during the previous 6 weekse. Nitrosoureas or Mitomycin C during the previous 6 weeksf. Other IMPs during the 4 weeks before treatmentg. Any prior treatment with a Chk1 inhibitor, or prior treatment with an ATR inhibitor within 6 months prior to receiving SRA737.2. Other malignancy within the past 2 years with the exception of adequately treated tumors that are associated with an expected 5 year disease-free survival of approximately 95% or better.3. Ongoing toxic manifestations of previous treatments greater than National Cancer Institute – Common Terminology Criteria for Adverse Events (NCI-CTCAE) Grade 1. Exceptions to this are alopecia or certain toxicities, which in the opinion of the investigator and the Sponsor or Sponsor's designee monitor should not exclude the subject.4a. For subjects in the Dose Escalation Phase that are not to be included in the Expansion Cohort, new or progressing brain metastases. Subjects with brain metastases that have been radiologically stable over an 8-week period may be included.4b. For subjects in the Cohort Expansion Phase, present or prior brain metastases.5. Women of childbearing potential (WOCBP) or women who are already pregnant or lactating. However, those patients who have a negative serum or urine pregnancy test before enrollment and agree to use two forms of contraception as per Appendix 4 or agree to sexual abstinence, effective from the first administration of SRA737, throughout the trial and for six months afterwards are considered eligible.6. Male subjects with partners of childbearing potential (unless they agree to take measures not to father children by using a barrier method of contraception as per Appendix 4 from the first administration of SRA737 through the trial and for 6 months after their final SRA737 dose). Men with pregnant or lactating partners must be advised to use barrier method contraception (eg, condom plus spermicidal gel) to prevent exposure of the fetus or neonate.7. Major surgery from which the subject has not yet recovered.8. At high medical risk because of nonmalignant systemic disease including active uncontrolled infection.9. Known to be serologically positive for hepatitis B, hepatitis C or human immunodeficiency virus (HIV).

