4.2.2 EXCLUSION CRITERIA

1. Have received the following prior or current anticancer therapy:
 - a. Radiotherapy within the last 6 weeks (except for symptom control and where the lesions will not be used as measurable disease)
 - b. Endocrine therapy during the previous 4 weeks except for luteinizing hormone releasing hormone (LHRH) agonists for prostate cancer

- c. Chemotherapy during the previous 4 weeks
- d. Immunotherapy during the previous 6 weeks
- e. Nitrosoureas or Mitomycin C during the previous 6 weeks
- f. Other IMPs during the 4 weeks before treatment
- g. Any prior treatment with a Chk1 inhibitor, or prior treatment with an ATR inhibitor within 6 months prior to receiving SRA737.

2. Other malignancy within the past 2 years with the exception of adequately treated tumors that are associated with an expected 5-year disease-free survival of approximately 95% or better.

3. Ongoing toxic manifestations of previous treatments greater than NCI-CTCAE Grade 1. Exceptions to this are alopecia or certain toxicities, which in the opinion of the investigator and the sponsor or sponsor's designee should not exclude the subject.

4a. For subjects in the Dose Escalation Phase that are not to be included in an Expansion Cohort: new or progressing brain metastases. Subjects with brain metastases that have been radiologically stable over an 8-week period may be included in this phase.

4b. For subjects in the Cohort Expansion Phase: present or prior brain metastases.

5. Women of childbearing potential (WOCBP) or women who are already pregnant or lactating. However, those patients who have a negative serum or urine pregnancy test before enrollment and agree to use two forms of contraception as per Appendix 4 or agree to sexual abstinence, effective from the first administration of SRA737, throughout the trial and for six months afterwards are considered eligible.

6. Male subjects with partners of childbearing potential (unless they agree to take measures not to father children by using a barrier method of contraception as per Appendix 4 from the first administration of SRA737 through the trial and for 6 months after their final SRA737 dose). Men with pregnant or lactating partners must be advised to use barrier method contraception (eg, condom plus spermicidal gel) to prevent exposure of the fetus or neonate.

7. Major surgery from which the subject has not yet recovered.

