5.5.1.3 Contraception Usage

To be eligible for this study, WOCBP (as defined per Appendix 4) and male subjects with partners of childbearing potential must use 2 forms of contraception or agree to sexual

abstinence effective from the first administration of SRA737 through the trial and for 6 months afterwards. See Appendix 4 for more information.

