7.2 EVALUATIONS DURING THE TRIAL

7.2.1 FIRST DOSE FOR PK (DAY -7 TO DAY -4) SCHEDULE

The sponsor may eliminate or modify the requirements for the Day -7 to Day -4 visit once sufficient data to evaluate the single-dose PK of SRA737 have been collected and analyzed. If this occurs, the modified requirements will be documented by an update to the Laboratory Manual.

Intensive PK assessments are outlined in detail in Section 7.7 or the Laboratory Manual. If required to facilitate the collection of PK, subjects may remain as in-patients for at least 24 hours after their first dose of SRA737 between Day -7 and Day -4.

The following assessments will be conducted predose on the first day of dosing unless performed within the preceding 3 days or unless noted otherwise below. Dosing should be delayed if the eligibility criteria are no longer met:

- Optional tumor biopsy for exploratory PD assays, if not done during screening (See Section 8.2.4)
- AEs and concomitant medications. AEs must be monitored and recorded in the eCRF from the first dose of SRA737 administration. At each visit, before each SRA737 administration, an assessment of any AE experienced since the previous visit must be made by the investigator, research nurse or suitably qualified member of the investigator's team.
 - The start and stop dates of the AE together with the relationship of the event to the SRA737 must be recorded in the medical records.
 - All AEs must be graded according to NCI-CTCAE v4.03. (See Section 10 for further details regarding AE reporting requirements).
 - Any concomitant treatment must be recorded in the medical records. (See Section 10 for further details regarding AE reporting requirements.)
- Height, weight, WHO performance status, temperature, pulse rate, seated BP.
- Laboratory tests (blood/urine/tissue samples):
 - Hematology: CBC with differential count
 - Biochemistry: Sodium, potassium, chloride, magnesium, adjusted calcium, phosphate, urea, creatinine, total protein, albumin, direct and indirect bilirubin, LDH, alkaline phosphatase, alanine aminotransferase and/ or aspartate aminotransferase, non-fasting glucose
 - Urinalysis: glucose, protein and blood
 - Pregnancy testing (WOCBP only): serum or urine test is acceptable. More frequent pregnancy tests may be conducted if required per local regulations.
 - Troponin: Troponin T or I (subject should be followed for the same parameter)

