Tumor Tissue for Optional Exploratory PD	Refer to Section 7.7 for time points									
Blood sample for PK				Refer to Section 7.7 for time points						
SRA737 administration				X (a)	Continuous daily dosing or as specified in alternate dosing schedule					
SRA737 Diary Card					Should be reviewed at each visit				X	

- a. Assessments scheduled to occur for the first dose for PK (given on a single day between Day -7 to Day -4) will be conducted on the first day of dosing unless performed within 72 hours prior or noted otherwise for the specific assessment in Section 7.2.1. Dosing should be delayed if eligibility criteria are no longer met. The Sponsor may eliminate or modify the requirements for the Day -7 to Day -4 visit once sufficient data to evaluate the single-dose PK of SRA737 have been analyzed.
- b. Monthly follow up is required for all SAEs and for those AEs considered drug related (highly probable, probable or possible) and present at the SFU visit. Monthly follow-up will continue until the event resolves, returns to baseline, stabilizes, or the subject discontinues from study.
- c. Only new SAEs assessed by the investigator as related to SRA737 and first subsequent anticancer therapy will be collected.
- d. Availability of suitable archival tumor tissue or planned biopsy for fresh tumor tissue acquisition for tumor profiling must be confirmed. When archival material was collected more than 18 months ago, the ability to collect fresh tumor tissue should be discussed with the sponsor. Submission prior to or during Screening (the 28-day window does not apply) with confirmation of positive results is required to determine eligibility for Expansion Cohort subjects. Archival tumor tissue should be requisitioned for submission by Cycle 1 Day 1 for Dose Escalation subjects. See Section 7.1.1 for more details. A blood sample for ctDNA tumor profiling will be obtained from all screened subjects within 28 days prior to the first dose. If prospective analysis is performed, results must be available prior to the first dose of SRA737. If retrospective analysis will be performed, results are not required to be available prior to the first dose of SRA737.
- e. For CRC subjects and other subjects as clinically relevant whose MSI status is unknown, determination of MSI status will be performed on archival tumor tissue or fresh tumor tissue submitted for tumor profiling during Screening.

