APPENDIX 3. NEW YORK HEART ASSOCIATION (NYHA) SCALE

Class I subjects with cardiac disease but without resulting limitation of physical activity; ordinary physical activity does not cause undue dyspnea (or fatigue, palpitation or anginal pain)

Class II subjects with cardiac disease resulting in slight limitation of physical activity; they are comfortable at rest; ordinary physical activity results in dyspnea (or fatigue, palpitation or anginal pain)

Class III subjects with cardiac disease resulting in marked limitations of physical activity; they are comfortable at rest; less than ordinary physical activity causes dyspnea (or fatigue, palpitation or anginal pain)

Class IV subjects with cardiac disease resulting in inability to carry out physical activity without discomfort; symptoms of dyspnea (or of angina) may be present even at rest; if any physical activity is undertaken, discomfort is increased.

APPENDIX 4. CONTRACEPTIVE GUIDANCE FOR WOMEN OF CHILDBEARING POTENTIAL (WOCBP) AND MALE PARTNERS OF WOCBP

The risks of treatment with SRA737 during pregnancy have not been evaluated. Please refer to the latest version of the Investigator's Brochure for additional information.

Women of Childbearing Potential

This protocol defines a women of childbearing potential (WOCBP) as a sexually mature woman who:

- Has not undergone a hysterectomy or bilateral oophorectomy, or
- Has not been naturally postmenopausal for at least 24 consecutive months (ie, has had menses at any time in the preceding 24 consecutive months). Of note, amenorrhea following cancer therapy does not rule out childbearing potential.

Contraceptive Requirements for Females and Female Partners of Male Subjects

In order to be eligible for the clinical trial, WOCBP planning to participate must agree to use 2 forms of contraception (one reliable form plus a barrier method) effective from the date of the first administration of SRA737 (ie, at least 7 days prior for hormonal methods) throughout the trial and for 6 months after the last dose of SRA737.

WOCBP partners of male subjects should use a reliable form of birth control from the date of the male partner's first administration of SRA737 (ie, at least 7 days prior for hormonal methods) throughout the trial and for 6 months afterwards.

The investigator should counsel subjects on appropriate methods for avoiding pregnancy during the study. These include the following:

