- Hormonal contraceptives (eg, combined oral contraceptives, patch, vaginal ring, injectables, implants) and condom;
- Intra-uterine device (IUD) or intrauterine system (IUS) and condom;
- diaphragms with spermicidal gel and condom

The following highly effective methods (failure rate <1% per year), are also acceptable as single methods:

- Vasectomy**
- Tubal sterilization*

Abstinence is only considered an acceptable method of contraception if it is a pre-existing part of a subject's lifestyle. Symptom-thermal methods (basal body temperature, cervical mucous, or calendar/rhythm) or withdrawal are not considered adequate forms of contraception for the purposes of this study.

*Tubal sterilization via the Essure procedure is not considered a reliable form of contraception unless tubal blockage is verified by hysterosalpingogram (HSP) approximately 3 months after microinsertion. Prior to verification, another contraception method described above should be used.

** Vasectomized partner is also considered a highly effective birth control method provided that the partner is the sole sexual partner of the WOCBP trial participant and that the vasectomized partner has received medical confirmation of the surgical success. Prior to verification, another contraception method described above should be used.

Contraceptive Requirements for Male Subjects with Female Partners of Childbearing Potential

All male study participants must agree to consistently and correctly use a condom plus spermicidal gel from the date of first administration of SRA737 throughout the trial and for 6 months after administration of the last dose of SRA737. If their female partner is a WOCBP as defined above, additionally, male subjects must be willing to ensure that their partner uses 1 of the methods of birth control listed above effective from the date of the first administration of SRA737 (ie, at least 7 days prior to the first dose for hormonal methods) throughout the trial and for 6 months after administration of the last dose of SRA737. Male subjects with pregnant or lactating partners must be advised to use condom plus spermicidal gel to prevent exposure of the fetus or neonate.

Male subjects must agree to refrain from sperm donation after the first administration of study drug and for at least 6 months after the last dose.

Procedures to be Followed in the Event of Pregnancy

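### Exclusion 5 and Section 5.5.1.3 admit a subject who newly promises sexual abstinence, but Appendix 4 accepts abstinence only if it already exists

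*Protocol*

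**What the plan says.** **Exclusion 5.** In Section 4.2.2, WOCBP with a negative pregnancy test escape the exclusion if they "agree to use two forms of contraception as per Appendix 4 or agree to sexual abstinence". The synopsis carries the same criterion and ends it: "or agree to sexual abstinence, effective from the first administration of SRA737, throughout the trial and for six months afterwards are considered eligible".

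**Section 5.5.1.3.** This section is also worded as an eligibility condition. It covers WOCBP and male subjects with partners of childbearing potential, who "must use 2 forms of contraception or agree to sexual" abstinence, running from first administration until six months after the trial. It closes by pointing to Appendix 4 for further information.

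**Appendix 4.** This too is framed as eligibility text: "In order to be eligible for the clinical trial, WOCBP planning to participate must agree to use 2 forms of contraception". It lists paired methods and two acceptable single methods, then says: "Abstinence is only considered an acceptable method of contraception if it is a pre-existing part of a subject's lifestyle". It also states: "The risks of treatment with SRA737 during pregnancy have not been evaluated".

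**Men.** Exclusion 6 asks for a barrier method in line with Appendix 4 and offers no abstinence option. Appendix 4 asks every male participant for a condom with spermicidal gel and states no exception.

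**Other references.** Section 10.6 requires two forms of contraception as set out in Appendix 4. Section 12.3 refers to the same appendix for the contraception information given at consent.

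**The concern.** Two parts of the protocol set eligibility rules on abstinence, and the rules differ. Under exclusion 5 and Section 5.5.1.3, what counts is a promise that takes effect at first dose. Under Appendix 4, what counts is an established practice. A site working from the criteria list and a site working from the appendix could decide differently about the same woman.

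What is at stake is subject safety. This is a first-in-human trial of a drug whose effects in pregnancy are unevaluated, and the appendix withholds acceptance from newly promised abstinence. Exclusion 5, followed as written, lets that method in.

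**Working it through.** No arithmetic applies. The check is to set the texts side by side and see which subjects each admits.

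**Step 1: what does the pointer to Appendix 4 qualify in exclusion 5?** The reference follows the two-forms option and comes before the word *or*. It governs how the two forms are chosen. Nothing after the *or* refers to the appendix.

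**Step 2: does Section 5.5.1.3 import the condition?** Its closing sentence sends the reader to the appendix for information. It does not say that abstinence counts only on the appendix's terms.

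**Step 3: can the timing be reconciled?** Exclusion 5 and Section 5.5.1.3 date the abstinence from the first dose. Appendix 4 requires it to exist already. A promise to start on the dosing day meets the first and fails the second.

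**Step 4: test cases, each a WOCBP with a negative pregnancy test.**

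| Subject | Exclusion 5 (synopsis, 4.2.2) | Section 5.5.1.3 | Appendix 4 |
|---|---|---|---|
| Uses a listed two-form combination | Eligible | Eligible | Acceptable |
| Already abstinent, agrees to continue | Eligible | Eligible | Acceptable |
| Not abstinent now, promises to abstain from first dose | Eligible | Eligible | **Method not acceptable** |

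The texts disagree in the third row only.

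**Step 5: men.** The only place that offers men abstinence is Section 5.5.1.3. Exclusion 6 does not, and the male requirements in Appendix 4 state no such exception. The abstinence sentence in Appendix 4 falls under the heading for females and female partners, and the appendix does not say whether it reaches male subjects. This is one loose end in Section 5.5.1.3.

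**The case against.** The best reply is that the body text is a summary and Appendix 4 is the detailed rule. Exclusion 5, Section 5.5.1.3, Section 10.6 and Section 12.3 all send the reader there. An already abstinent woman satisfies every place, so the texts can be met together by applying the stricter one. Counting places does not settle the matter either, since the synopsis simply repeats Section 4.2.2.

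Most of this stands as evidence of intent: the stricter rule is very probably what the sponsor wants. It does not remove the conflict, because none of the four pointers makes the abstinence option conditional. Section 10.6 speaks only of two forms and does not mention abstinence.

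There are also safeguards. The sponsor or its designee confirms eligibility before enrollment (Section 4). Investigators must make every effort to prevent pregnancy, and treatment stops at once if a subject becomes pregnant (Section 10.6). Appendix 4 provides for counseling and requires subjects to report a known or suspected pregnancy. These limit the harm but do not tell a site which abstinence rule to apply.

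A reader might infer two stronger points that the documents do not support:

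- **That sparse pregnancy testing during treatment measures the harm.** The testing schedule is the same for every WOCBP, whatever her method. The abstinence wording does not cause it, and correcting that wording would not change it.
- **That the male rules are a second contradiction.** Exclusion 6 already refers to Appendix 4 for the barrier method. The two forms in Section 5.5.1.3 can be read as a condom plus the partner's method. Only the abstinence option in Section 5.5.1.3 is out of line, so exclusion 6 needs no rewrite.

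**Conclusion.** The inconsistency is real and narrow. Exclusion 5 (both places) and Section 5.5.1.3 admit a WOCBP who newly promises abstinence, and Appendix 4 rejects her method. It is a wrong eligibility rule, not just missing detail, because a site that follows exclusion 5 exactly enrolls a subject on a method that the protocol elsewhere declines to accept.

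The documents give no count of affected subjects. The number is probably small: the appendix's WOCBP definition leaves out women after hysterectomy or bilateral oophorectomy and those naturally postmenopausal for at least 24 months, and one of the six expansion cohorts is prostate cancer. That is a judgment, not a figure from the plan.

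The conclusion rests on reading exclusion 5 as punctuated, with the appendix reference attached to the two-forms option. It also assumes that the stricter rule is the intended one. If the sponsor instead means to accept newly promised abstinence, Appendix 4 is the text to change. Severity is the lowest, with no effect on sample size, endpoints or analysis.

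**What to change.** 1. In exclusion 5, in the synopsis and in Section 4.2.2, change the second option to *sexual abstinence, only where pre-existing as Appendix 4 requires*.
2. Make the same change for WOCBP in Section 5.5.1.3. For men in that section, replace the abstinence option with a reference to the male requirements in Appendix 4.
3. Check that the eligibility checklist and the consent form carry the same rule.

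This means wording edits in three places plus the two document checks. Visits, tests and analyses stay as they are. The downside is that WOCBP who newly promise abstinence, probably few but uncounted, would need two contraceptive forms or one of the listed single methods in order to enroll.

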5.5.1.4 QT Prolonging Drugs

Preclinical data indicates that SRA737 possesses a minimal risk of clinically relevant prolongation of the QTc interval. The potential for QT prolongation has not yet been evaluated in the clinical setting. As a result, caution should always be used when continuing or initiating administration of QT prolonging drugs (<https://www.crediblemeds.org>) and summary list of applicable drugs for this study is provided in Appendix 5.

5.5.1.5 Acid-reducing Agents

Preliminary in vitro studies suggest that the SRA737 citrate drug product may possess some minimal to moderate pH-dependent solubility over the physiological range. The effect of acid-reducing agents on the oral bioavailability of SRA737 in preclinical species or in humans is currently not known. Consequently, administration of antacids or H₂ antagonists should occur 4 hours before or 2 hours after administration of SRA737. Due to the long-acting duration of proton pump inhibitors (PPIs), there is no utility in separating SRA737 and PPI dose administrations. PPIs should therefore be avoided if possible and used with caution if necessary.

